## **Statistical Analysis and Methods**

### **Behavioral Outcomes analysis**

The Beck Depression Inventory-II and the Spielberger State-Trait Anxiety Inventory will be used to evaluate acute changes in mood and anxiety symptoms. Behavioral data will be analyzed using repeated measures ANOVA [mood and anxiety ratings by time (PRE-, POST-stimulation) and session (exhalation-gated, inhalation-gated)], controlled for baseline.

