## Clinical Assessments

Outcomes will include whether acute stimulation with tVNS reduces mood symptoms. Our group has found tVNS diminishes anxiety in an acute paradigm. Measures at intake will include: Structured Clinical Interview for DSM Disorders, Hamilton Rating Scale for Depression 17, and the Montgomery Asperger Depression Rating Scale. Before and after tVNS/fMRI, we will assess mood with the Beck Depression Inventory-II, Hamilton Rating Scale for Depression 17, Spielberger State-Trait Anxiety Interview, and a Visual Analog Scale.

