## **Blood Draw**

Our on-site Phlebotomist will draw one sample [(approximately 5 teaspoons (26 ml)] at the beginning and another blood sample [approximately 3 teaspoons (13 ml)] after each of the two imaging visits. Previous studies from our group have demonstrated gonadal hormonal regulation of mood and autonomic nervous system circuitry. In addition, a significant body of evidence has suggested an interrelationship between the activity of the autonomic nervous system, particularly the vagus nerve and the immune system. We will use estradiol, progesterone, cytokines (IL-1 $\beta$ , IL-6, IL-10, TNF $\alpha$ ), and C-reactive protein (CRP) levels as covariates in the analysis of tVNS effects in the activation of brain regions related with mood and autonomic modulation. The results of the blood tests are not clinically relevant to individual persons; therefore, we will not return results to the subject. However, when the study analyses are complete, we will make study results available to the subject, if desired (although individuals are not identified in these analyses).

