## **Saliva Collection**

We would like to collect a sample of saliva (15 ml saliva tube) to examine cortisol levels in order to evaluate the state of the hypothalamic-pituitary-adrenal (HPA)-axis in depressed subjects. Collection will take place the evening before the scan (11pm), prior to the scan, and 60 minutes following the picture task. This variable will be considered in the analysis of the effects of our intervention in the modulation of the stress response circuitry and central autonomic network. The samples will have no personal identifying information and will be placed in a storage bank in secure buildings in the Boston medical area that have limited access. They will be used only for research that is carefully reviewed and approved both by this study and the Institutional Review Board.

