## **Scanning**

Subjects will be randomized as to the order of scan dates (inhalation-gated vs. exhalation-gated), which will be separated by at least one week. Scanning begins with the subject at full rest then they will undergo our mild visual stress paradigm for 18 minutes. Then the electrodes will be placed. The stimulation block will have a total duration of 30 minutes. The electrodes will be withdrawn at 20 minutes after and the mild visual stress task repeated. Patients will first undergo a mild stress task where they view pictures during fMRI scanning. Our fMRI stress paradigm has been described in detail previously and conducted in healthy subjects, MDD, and psychotic cases. Briefly, subjects view 3 stimulus blocks (6 images per block) for 30 seconds (1 image every 5 seconds) in the following order: fixation, neutral, and negative images (see definitions below). Subjects view this sequence 4 times during each of 3 runs for a total of 72 images (24 images per condition per run), and press a button each time a new image appears in order to ensure attention to the images, without adding cognitive load. Images were drawn from the International Affective Picture System (IAPS) according to affective valence and arousal (negative = unpleasant + high arousal, neutral = neutral + low arousal). Fixation images are based on Fourier transformations of each neutral image to create an image with the same physical properties of the original but without recognizable content. The stress task will be repeated after the tVNS portion of imaging. When the fMRI session is complete, subjects will be shown two blocks of negative and neutral images sampled from the set shown during imaging and will be asked to provide subjective ratings of arousal using the Self-Assessment Manikin (SAM).

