## **Post-Scan Follow Ups**

After each fMRI scan we will follow up with each subject to assess their mood. We will follow up one day and seven days after each scan. The follow-ups one day after the scan will consist in the administration of a Visual Analogue Scale for mood states through a REDcap online survey. For the 7th day follow-ups we will administer the Hamilton Depression Scale, Beck Depression Inventory-II, Spielberger State-Trait Anxiety Interview, and the Visual Analog Scale. The first 7th day follow up will be conducted in person at Imaging Visit #2. The second 7th day follow up will be conducted by phone. These follow ups will evaluate acute changes in mood following tVNS administration during the imaging visits.

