### **Sample Size (Power Analysis)**

The present study will recruit a total of 20 subjects (women age 25-40 with recurrent MDD). This will allow for the possibility of unusable data due to subject motion during scanning, scanner artifact problems as well as problems with the collection of behavioral data and human error.

Group size power statistics: In a previous study of manual acupuncture (N = 11), we were able to detect changes in activation of limbic and subcortical gray structures in the approximate range of -0.7% to -0.2%.

Also based on previous data (amygdala, manual acupuncture stimulation), we will assume a standard deviation of BOLD signal change of 2.5% for the purpose of power calculation and sample size determination. We do not consider temporal autocorrelation in the power calculations that follow, though we will take autocorrelation into account during the data analysis.

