### **Magnetic resonance imaging data analysis**

Comparisons of interest in the fMRI analysis (BOLD signal changes during exposure to negative vs neutral images) will be tested using linear contrasts and results from the individual subject level will be submitted to a second-level factorial analysis with two factors: time of visual stress task (PRE- or POST-stimulation) and stimulation session (exhalation-gated or inhalation-gated). Significant interactions between these factors will be submitted to post-hoc analyses to determine directionality of the effect. Due to our a priori hypothesis of specific effects of tVNS on stress response circuitry, the analysis will be restricted to specific regions of interest (ROIs) using a small volume correction approach. A voxel-wise height threshold of  $p < 0.001$  (uncorrected for multiple comparisons), and a cluster correction with FWE  $p$ -value  $< 0.05$  will be applied. Mean beta weights within each significant cluster will be extracted for each participant using the REX toolbox and will be included in regression analyses in STATA (StataCorp, College Station TX) to investigate the link between variations in stress response circuitry activity and changes in depressive symptoms (BDI score difference: POST-PRE) after tVNS administration. Adjusted regression coefficients will be calculated after including baseline BDI scores and use of antidepressant medications in the models.

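### Session order is randomised, but the exhalation-versus-inhalation analyses name no visit-order term; adding one is a cheap, low-priority gain in precision, not the repair of an error

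*Combined protocol and SAP*

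**What the plan says.** The Scanning section makes this a two-period crossover: "Subjects will be randomized as to the order of scan dates (inhalation-gated vs. exhalation-gated", with sessions at least a week apart. It gives neither the method of randomisation nor a target split.

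The comparisons between sessions are these:

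- **Behavioral Outcomes analysis:** "Behavioral data will be analyzed using repeated measures ANOVA [mood and anxiety ratings by time (PRE-, POST-stimulation) and session (exhalation-gated, inhalation-gated)], controlled for baseline". The section does not say which baseline is meant. Clinical Assessments does not list the BDI-II at intake but does say "Before and after tVNS/fMRI, we will assess mood with the Beck Depression Inventory-II", so a session PRE rating is the likely reading.
- **Magnetic resonance imaging data analysis:** a "second-level factorial analysis with two factors: time of visual stress task (PRE- or POST-stimulation) and stimulation session (exhalation-gated or inhalation-gated", with a voxel height threshold of p < 0.001 and a cluster correction. The same section compares connectivity between the two session types, both during the stimulation runs and during the picture task.
- **Cardiac Autonomic Analysis:** names an outcome but no group-level model, so there is not yet a model to which an order term could be added.

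Other covariates are named. Hormone, cytokine and CRP levels will be used as "levels as covariates in the analysis of tVNS effects in the activation of brain regions related with mood and autonomic modulation". Salivary cortisol will be "considered in the analysis of the effects of our intervention in the modulation of the stress response circuitry". Baseline BDI and antidepressant use enter the brain-mood regressions. None of these is visit order.

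**The concern.** In a two-period crossover, the first and second visits can differ for reasons unrelated to the gating: familiarity with the scanner, the picture task or the stimulation. If the PRE-to-POST change differs by visit and the model ignores this, two things follow. The difference inflates the error against which the session contrast is tested, and, if more women have one order than the other, part of it is attributed to gating. Aim 3 rests on this contrast in at most 20 women, and the sample-size section expects some unusable data.

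The covariates do not stand in for order. A value measured once per woman, or her antidepressant use, drops out of her own between-session difference. Blood markers and cortisol may absorb some visit-to-visit variation, but they are planned for the brain analyses and do not code visit.

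Not every visit difference matters. In an analysis of change, a shift that is equal in PRE and POST cancels from the time-by-session interaction; for fMRI, so does a shift that is equal for negative and neutral images. What remains is a visit effect on the change or, for stimulation-run connectivity, which has no PRE value, any shift in level.

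**Working it through.** The plan gives no figure for a visit effect, so there is none to reproduce.

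**Inputs.** From the documents: n = 20; BOLD changes of 0.2% to 0.7% and an SD of 2.5% ("we will assume a standard deviation of BOLD signal change of 2.5% for the purpose of power calculation and sample size determination"), hence effect ratios 0.2/2.5 = 0.08 and 0.7/2.5 = 0.28 if that SD applied to this contrast. Assumed: two-sided 5% test, all 20 analysed, simple or 10:10 allocation, and a session effect of 0.65 SD (power near 80%).

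**Model.** For each woman, D = (POST-PRE, exhalation) minus (POST-PRE, inhalation) = τ + s·p + e. Here s = +1 if exhalation came first and -1 otherwise, p is the visit-1 minus visit-2 difference in the change, and SD(e) = 1.

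**Without an order term.** The mean of D estimates τ + p(n1-n2)/n. The shift is 0 at 10:10, 0.2p at 12:8 and 0.4p at 14:6. Under simple randomisation a split of 14:6 or worse has probability 11.5%. The expected variance of D rises to 1 + 4p²n1n2/[n(n-1)]; at 10:10 and p = 0.5 this is 1 + 0.25×400/380 = 1.26, so the SE is about 12% larger.

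**With the term.** The intercept has SE 0.5√(1/n1+1/n2) on 18 df. At 10:10 this is 0.224, equal to 1/√20, so only a degree of freedom is lost. At 14:6 it is 0.244.

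**Power (%), without v with the term:**

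| p | Effect 0.65, simple | Effect 0.65, 10:10 | Effect 0.28, simple |
|---|---|---|---|
| 0 | 78.7 v 76.2 | 78.7 v 78.5 | 22 v 21 |
| 0.25 | 76.3 v 76.2 | 76.8 v 78.5 | 21.1 v 21.2 |
| 0.5 | 69.3 v 76.2 | 70.8 v 78.5 | 18.6 v 21.2 |

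At effect 0.08, the term changes average power by under 0.5 points for any p up to 0.8.

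**Type I error without the term.** It averages about 5% under simple randomisation. Given the split, at p = 0.25 and 0.5, it is 4.4% and 2.9% at 10:10, and 6.4% and about 9.7% at 14:6.

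**Break-even p (simple / 10:10 or equal split).** About 0.25 / 0.09 with 20 analysed, 0.29 / 0.115 with 16 and 0.35 / 0.16 with 12. For one voxel at p < 0.001 and n = 20 it is about 0.28 / 0.14. None of these figures carries over to the cluster-corrected test.

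**Form of the model.** An analysis of all four cells with period and period-by-time, but with subject as the only blocking factor, gives the same point estimate and a different test. It uses a pooled residual on 80-25 = 55 df. With assumed variances of 1 (subject), 0.5 (visit) and 0.5 (residual) at 10:10, its type I error is about 1.3% and its power 63%, against about 5% and 79% for the regression on D.

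**Baseline control.** If the baseline is the session PRE rating and no code is included, a visit effect on POST alone remains in full. The share of a PRE-only effect that remains equals the fitted slope: about 27% with visit and residual variances 0.3 and 0.7, and 73% with 0.8 and 0.2. The documents give neither variance. Part of a constant visit shift, which change scores would cancel, also re-enters.

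**The case against.** The case against is substantial. Randomising the order already protects the comparison. The documents give no reason to place the visit effect above 0.25 SD, and below that the term loses power on average under simple randomisation. The larger gains rest on an assumed session effect of 0.65 SD; at the ratios implied by the sample-size section, power is near 21% or lower whichever model is used. The brevity of the connectivity paragraph need not mean that order was deliberately left out. All of this stands, and it is why the point is a refinement. What it does not remove is the favourable balance if order is balanced: a loss of 0.3 points at most against a gain of 7.7 at p = 0.5 (effect 0.65).

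A reader might infer more: that leaving out the term biases Aim 3 or inflates its error rate. The documents do not support that. Order is randomised, so the expected bias is zero and average type I error is about 5%; the shift arises only given an unequal realised split and a non-zero visit effect.

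A reader might also take the timing of the first seven-day assessment ("day follow up will be conducted in person at Imaging Visit #2") as showing carry-over into the second session's PRE rating. It shows only that the two assessments fall at the same visit. An order term would in any case remove only carry-over common to both orders.

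**Conclusion.** The plan is valid on average as written. It omits a standard term that would protect the precision of the Aim 3 contrast and remove the shift p(n1-n2)/n that an unequal split would produce. This is a low-priority improvement. Whether it gains or loses power depends on a visit effect whose size the documents do not give: the break-even is about 0.25 SD of the within-woman session difference under simple randomisation and 0.09 SD at 10:10. Those thresholds hold for one two-sided 5% test with 20 women analysed, and rise with fewer women or at the fMRI voxel threshold. The case for the term is strongest if the order split is kept close to equal.

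**What to change.** Specify the following before any session data are examined:

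- For the mood ratings, the second-level fMRI contrast and picture-task connectivity, regress each woman's double difference on an intercept and a sequence code (+1 exhalation first, -1 inhalation first), and test the intercept.
- For stimulation-run connectivity, do the same with the simple session difference.
- Do not mean-centre the code. Under simple randomisation at p = 0.5, centring gives type I error of about 7.5%, and a 0/1 code about 32%, because its intercept refers to one sequence only.
- If a mixed model or ANOVA is preferred, include period and period-by-time, with subject-by-session and subject-by-time error terms. Period alone does not adjust the interaction.
- State which baseline the behavioural analysis uses. If it is the session PRE rating, regress the POST difference on an intercept, the PRE difference and the same code.

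The change is to analysis wording and needs no new data. It costs one degree of freedom, beyond any used by the blood and cortisol covariates. With no visit effect and a session effect of 0.65 SD, the power loss is about 2.5 points averaged over simple randomisation: 0.3 at 10:10, 1.9 at 12:8 and 7.5 at 14:6. Differential carry-over remains.

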### **Magnetic resonance imaging data analysis**

Comparisons of interest in the fMRI analysis (BOLD signal changes during exposure to negative vs neutral images) will be tested using linear contrasts and results from the individual subject level will be submitted to a second-level factorial analysis with two factors: time of visual stress task (PRE- or POST-stimulation) and stimulation session (exhalation-gated or inhalation-gated). Significant interactions between these factors will be submitted to post-hoc analyses to determine directionality of the effect. Due to our a priori hypothesis of specific effects of tVNS on stress response circuitry, the analysis will be restricted to specific regions of interest (ROIs) using a small volume correction approach. A voxel-wise height threshold of  $p < 0.001$  (uncorrected for multiple comparisons), and a cluster correction with FWE  $p$ -value  $< 0.05$  will be applied. Mean beta weights within each significant cluster will be extracted for each participant using the REX toolbox and will be included in regression analyses in STATA (StataCorp, College Station TX) to investigate the link between variations in stress response circuitry activity and changes in depressive symptoms (BDI score difference: POST-PRE) after tVNS administration. Adjusted regression coefficients will be calculated after including baseline BDI scores and use of antidepressant medications in the models.

Functional connectivity will be evaluated during tVNS stimulation runs by extracting fMRI time series from the selected ROIs and using them in a weighted GLM and semi-partial correlation analyses. Resultant whole-brain parameter estimates and their variance from each individual will be passed to group-level analyses to evaluate connectivity differences between exhalatory- and inhalatory-gated sessions. For evaluation of functional connectivity during IAPS, the extracted fMRI time series from the selected ROIs and its interaction with the regressors for negative and neutral content will be used to evaluate connectivity differences between the visual stress tasks during PRE- and POST-stimulation, for exhalatory- and inhalatory-gated sessions. General linear models (GLM) will be conducted in STATA (StataCorp, College Station TX) to investigate the link between variations in functional connectivity and changes in depressive symptoms in response to tVNS administration. Adjusted regression coefficients will be calculated after including baseline BDI scores and use of antidepressant medications in the models.

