## **II. SPECIFIC AIMS**

Major Depressive Disorder (MDD) is a leading cause of morbidity and mortality worldwide. Abnormalities in vagal tone are more common in MDD, particularly loss of parasympathetic cardiac regulation, and increase the risk for cardiovascular disease (CVD). Vagal nerve stimulation (VNS) is an FDA approved treatment for MDD that modulates circuitry implicated in mood regulation. However it is unclear whether therapeutic benefit of VNS on mood, can also reduce cardiac morbidity and mortality. The circuits for autonomic cardiac regulation overlap with those for mood regulation, but modulation of ANS has not been directly associated with mood response. As a first step, we will identify whether VNS effects on mood circuitry in MDD are associated with modulation of vagal tone and mood.

In the proposed study in MDD patients, we will 1) identify the neural circuitry associated with tVNS, 2) identify its acute effects on heart rate variability, and 3) assess the impact of brain activity and ANS function on mood. We will control for factors known to impact vagal tone, in particular gonadal hormones in women. This is the first study to map the neurobiology of mood and vagal response to VNS using a less invasive form of VNS that may have a wider application.

**Specific Aim 1:** To determine the acute effects tVNS on cerebral blood flow in MDD patients.

Hypothesis 1: During real tVNS/fMRI interleaving, tVNS will deactivate amygdala, parahippocampal gyrus, hippocampus, posterior cingulate, and precuneus and will activate insula, thalamus and anterior cingulate.

Hypothesis 2: Brain activity deficits in stress response circuitry in MDD will be attenuated following 20 minutes of tVNS, in hypothalamus, amygdala, hippocampus, and anterior cingulate gyrus.

**Specific Aim 2:** To determine the acute effects of tVNS on vagal tone and mood in MDD patients.

Hypothesis 1: tVNS will increase high frequency R-R variability and decrease mood symptoms compared to baseline.

**Specific Aim 3:** To compare the effects of exhalation-gated tVNS with inhalation-gated tVNS on cerebral blood flow, vagal tone and mood regulation in MDD patients.

Hypothesis 1: Exhalation-gated tVNS will have a significant greater impact on regulation of cerebral blood flow, vagal tone and mood in MDD patients compared to inhalation-gated tVNS.

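### The activation-to-mood regression is run only on clusters that already show a significant group effect, with no fallback if none does

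*Combined protocol and SAP*

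**What the plan says.** Section II lists among the study's purposes to "assess the impact of brain activity and ANS function on mood". Aim 1 Hypothesis 2 names the stress-circuit regions in advance: hypothalamus, amygdala, hippocampus and anterior cingulate.

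Section VI, Magnetic resonance imaging data analysis, sets up a factorial model of time (before or after stimulation) by session (exhalation- or inhalation-gated). On where effects are sought, "the analysis will be restricted to specific regions of interest (ROIs) using a small volume correction approach", but the regions are not listed there. The threshold is "A voxel-wise height threshold of $p < 0.001$ (uncorrected for multiple comparisons"), "and a cluster correction with FWE" p below 0.05. Then "Mean beta weights within each significant cluster will be extracted for each participant using the REX toolbox", and these values enter regressions "to investigate the link between variations in stress response circuitry activity and changes in depressive symptoms (BDI score difference: POST-PRE) after tVNS administration". On covariates: "Adjusted regression coefficients will be calculated after including baseline BDI scores and use of antidepressant medications in the models".

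The section does not say what is regressed if no cluster is significant, or which effect (time, session or interaction) defines the clusters. The functional-connectivity paragraph that follows describes a second set of models, relating connectivity to symptom change. Their time series come from the selected ROIs, with no stated condition that those ROIs first show significant activation.

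**The concern.** A group-mean effect and a between-woman association are different quantities. If regional response rises in women who improve and falls in women who do not, the mean change can be near zero while the association with mood is strong. Followed as written, the plan would then find no cluster, extract nothing, and leave that association unexamined. The individual-difference question depends on a result that it does not need, although the regions of interest were named beforehand.

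There is a second, smaller effect. A cluster passes when its t statistic is large, which favours samples in which the betas happen to vary little between women. Less spread in the predictor means a lower correlation and less power in the regression that follows.

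**Working it through.** **The plan's own figure.** Section VI, Sample Size, gives N = 20 but no alpha, power or target difference. It announces power calculations, and none follow. There is therefore no power figure to reproduce.

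**Inputs from the documents.** N = 20. Earlier acupuncture study (N = 11): changes "in the approximate range of -0.7% to -0.2" per cent. Assumed SD 2.5%, with no statement whether this is between women or over time. Four regions in Aim 1 Hypothesis 2.

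**Assumptions.** The four regions are independent; one t-test per region stands in for voxel and cluster inference; no data are lost; the true brain-mood correlation is 0.50; the two covariates are left out.

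**Step 1. Chance that a cluster passes, with 2.5% as the between-woman SD of the contrast.** Standardised effect d = 0.7/2.5 = 0.28 at the top of the range and 0.2/2.5 = 0.08 at the bottom. Noncentrality = d × √20 = 1.25 and 0.36, on 19 degrees of freedom. The chance for any of four regions is 1 − (1 − p)^4.

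| Proxy for the gate | p per region, 0.7% | Any of four, 0.7% | Any of four, 0.2% |
|---|---|---|---|
| 0.001 one-sided per region | 2.35% | 1 − 0.9765^4 = 9% | 1% |
| 0.05 two-sided, shared (0.0125 each) | 8.9% | 1 − 0.9106^4 = 31% | 7% |
| 0.05 two-sided per region | 22.1% | 1 − 0.7787^4 = 63% | 23% |

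The first row is stricter than the plan's rule: under the null it passes any of four regions in 1 − 0.999^4 = 0.4% of trials, against a nominal 5% for one family-wise correction. The last row passes 1 − 0.95^4 = 18.5% under the null.

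**Step 2. The other reading, with 2.5% as volume-to-volume noise.** Each image condition lasts 3 runs × 4 blocks × 30 s = 360 s; at TR 1.25 s that is 288 volumes. Per-woman SD of a negative-minus-neutral contrast: 2.5 × √(2/288) = 0.208%. Of its POST-PRE change: 0.208 × √2 = 0.295%. Of the time-by-session interaction: 0.295 × √2 = 0.417%. Ignoring true variation between women and autocorrelation, with n = 20, the pass chance per region is:

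- POST-PRE change: 33% (0.2% effect) to about 100% (0.7%) at 0.001, and 82% to about 100% at 0.05.
- Interaction: 12% to about 100% at 0.001, and 53% to about 100% at 0.05.

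**Step 3. What selection does to the regression when a region passes.** Simulation with n = 20, d = 0.28 and true correlation and slope both 0.50 on the standardised scale:

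| | Unselected | 0.05 gate | 0.001 gate |
|---|---|---|---|
| SD of betas relative to true SD | about 0.99 | 0.92 | 0.81 |
| Mean correlation | 0.49 | 0.46 | 0.42 |
| Mean slope | 0.50 | 0.50 | 0.50 |
| Power | 64% | 59% | 49% |
| Type I error (true correlation 0) | 5% | 5% | 5% |

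At d = 0.8 under the 0.001 gate a region passes in about 52% of trials, and the correlation is 0.47 against 0.49.

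**Step 4. Both stages together, for one region at 0.7%.** The chance of passing and then finding the association is 0.221 × 0.585 = 13% under the 0.05 gate and 0.0235 × 0.488 = 1.1% under the 0.001 gate. An ungated regression has 64%, provided that the regional mean carries the same correlation.

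**The case against.** Three stronger readings are tempting, and the documents do not support them.

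*The brain-to-mood aim as a whole is usually untestable.* The connectivity-mood models use the selected ROIs and are not written as conditional on significant activation, so a brain-mood analysis survives when no cluster passes. This stands. It limits the point to activation; connectivity is a different measure and does not replace the promised regression on regional activity.

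*In about nine trials out of ten there is nothing to regress.* That figure needs 2.5% to be a between-woman SD and a gate stricter than small-volume cluster correction. The Sample Size section's remark on temporal autocorrelation leaves the time-series reading open, and the section reports detecting such changes with 11 subjects. The factorial model also offers more than one effect that could define a cluster. This stands too: the frequency cannot be fixed from the documents.

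*The estimates are biased, or false positives are inflated.* The clusters are selected on the predictor's group mean, not on its relation to BDI. The plan reports regression coefficients, and the slope stays at 0.50 with type I error near 5%. Only the correlation and the power fall.

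The gain from the remedy is also not guaranteed. If averaging over a whole region dilutes the true correlation from 0.50 to about 0.43, power at n = 20 is about 49%, the same as after the 0.001 gate. That cancels the gain among trials in which a cluster passes. It does not touch the main gap, which is that no activation regression exists when none passes.

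**Conclusion.** The point holds for the activation-to-mood regression. As written, that analysis exists only if the group-mean test succeeds, so an association without a mean effect goes unexamined. This follows from the text and needs no numerical assumption.

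Its frequency does need assumptions. With a between-woman SD of 2.5%, an effect of 0.7%, n = 20 and four independent regions, at least one region passes in 9%, 31% or 63% of trials according to how the threshold is represented; at 0.2% the figures are 1%, 7% and 23%. With 2.5% as time-series noise, passing can be likely. The loss from selection itself is moderate: at 0.7%, correlation 0.42 to 0.46 instead of 0.49, and power 49% to 59% instead of 64%.

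This is a worthwhile and inexpensive improvement to one of two brain-mood analyses, not a failure of the whole aim.

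**What to change.** In Magnetic resonance imaging data analysis, define masks for the four regions of Aim 1 Hypothesis 2 (hypothalamus, amygdala, hippocampus, anterior cingulate). Name the contrast from which betas are taken, since the section leaves this open. Extract the mean beta in each mask for every woman with usable data, and run the BDI-change regressions on these with the planned covariates, whatever the group-level result. Keep the significant-cluster regressions as a supplement, labelled as conditional on the group result.

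The cost is a mask definition and a sentence or two before analysis, with no new data. The downside is that whole-region averages may dilute a focal effect; the supplementary cluster regressions partly cover this when a cluster is found.
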